9.2 Other Medical Device or Medication Specified for Use during the Study

No other medical devices or medications are required to be used in conjunction with the treatments during the clinical study.

9.3 Treatment Assignment / Randomization

Only after signing the ICF, a subject will be assigned a subject number by the electronic data capture system.

Document: TDOC-0054 099 **Version:** 2. 0; Most-Recent; Effective; CURRENT

Status: Effective Page 41 of 71

9.4 Treatment masking

All members associated with the study (at the site and the Study Sponsor) are unmasked to the assigned treatment.

9.5 Accountability Procedures

Upon receipt of IPs, the Investigator or delegate must conduct an invento 1y of ACRYSOF IQ PanOptix Presbyopia Con ecting IOL, Model TFNT00 by serial number, complete study-specific confilmation of receipt procedures as described in the MOP, and retain any required documentation in the Investigator's clinical study records. Throughout the study, the Investigator or delegate must maintain records of IP use and collection for each subject. This record must be made available to the study monitor for the purposes of verifying the accounting of IP supplies. Any discrepancies and/or deficiencies between the observed disposition and the written account must be recorded along with an explanation. All IPs sent to the Investigator must be accounted for by Study Sponsor personnel, and in no case be used in an unauthorized manner.

 Return to the Study Sponsor investigational and control products associated with a device deficiency. Refer to Section 11 of this protocol for additional information on the reporting of device deficiencies and to the MOP for information on return of study products associated with these events.

The Investigator is responsible for proper disposition of all unused IPs at the conclusion of the study, according to the instructions provided in the MOP.

9.6 Changes to concomitant medications, treatments/procedures

After the subject is enrolled into the study, the Investigator must instruct the subject to notify the study site about:

- Any new medications
- Alterations in dose or dose schedules for cunent medications,
- Any medical procedure or hospitalization that occurred or is planned
- Any non-dtug therapies (including physical therapy and blood transfusions).

The Investigator must document this inf01mation in the subject's case hist01y source document s.

Document: TDOC-0054 099 Vers ion: 2. 0; Most-Recent; Effective; CURRENT

St atu s: Effective Page 42 of 71

Effective Date: 13-Dec -2017

10 STUDY PROCEDURES AND ASSESSMENTS

10.1 Informed Consent and Screening

The Investigator or delegate must explain the purpose and nature of the study, and have the subject or legally authorized representative read, sign, and date the IRB/IEC-approved infmmed consent document. The delegate should be a licensed medical doctor of ophthalmology. The subject must sign the ICF BEFORE any study-specific procedures or assessments can be performed, including study-specific screening procedures. Additionally, have the individual obtaining consent from the subject and a witness, if applicable, sign and date the info1med consent document. The subjects should be provided with enough time for his/her decision on participation on the trial, and shouldhave options to discuss with his/her family members or relatives about the participation to the investigation.

The Investigator or delegate must provide a copy of the signed document to the subject and place the original signed document in the subject's chart, or provide documentation as required by local regulations.

10.2 Description of Study Procedures and Assessments

Effectiveness assessments:

Below assessments will be conducted in the photopic lighting condition except subjective symptoms,

- Distance VA(4 m),
 - o Monocular (1st and/or 2nd eye) UCDVA
 - Binocular UCDVA
 - o Binocular BCDVA
- Intelmediate VA(60c m)
 - o Monocular (1st and/or 2nd eye) UCIVA
 - o Binocular UCIVA
- Near VA (40 cm)
 - o Mono cular (1st and/or 2nd eye) UCNVA
 - o Binocular UCNVA
- Binocular defocus curve

Document: TDOC-0054 099 **Version:** 2. 0; Most-Recent; Effective; CURRENT

St atu s: Effective Page 43 of71

- •
- •
- Bestcon-ected binocular contrast sensitivity with & without glare
- Subjective symptoms

Safety assessments:

- Adverse Device Events including Secondally Surgical Interventions (SSIs) related to the optical propelties of the IOL
- Device deficiencies
- Fundus examination and fundus visualization
- Intraocular pressure
- Slit-lamp examination
- IOL obselvations
- Surgical problems
- Subjective posterior capsule opacification
- Posterior capsulotomy
- Lens decentration and tilt

Preoperative assessments:

- Uline PregnancyTest
- •

Detailed descriptions of assessments and procedures are provided in the MOP. The Investigator is responsible for ensuring responsibilities for all procedures and assessments are delegated to appropriately qualified site personnel.

10.2.1 Demographics

Obtain demographic inforniation including age, race, ethnicity, height,- and sex.

10.2.2 Medical History

Collect medical hist01y info1mation, including info1mation on all medications used within the past 30 days. Include herbal therapies, vitamins, and all over-the-counter medications as well

Document: TDOC-0054099 Version: 2.0; Most-Recent; Effective; CURRENT

Status: Effective Page 44 of 71

as prescription medications. Throughout the subject's participation, obtain information on any changes in medical health and/or the use of concomitant medications.

10.2.3 Concomitant Medication

Concomitant medications can be ocular or nonocular. Details are provided in the MOP.

10.2.4 Inclusion/Exclusion Criteria

At the conclusion of Visit 0, verify the subject meets all eligibility criteria as detailed in the protocol, Section 8.1 Inclusion Criteria and Section 8.2 Exclusion Criteria.

10.2.5 Investigational Product compliance

N/A

10.2.6 Urine Pregnancy Test

For women of childbearing potential, request a urine pregnancy test be taken at the Investigator's office.

10.2.9 Visual Acuity: Effectiveness Assessment

ETDRS visual acuity testing for both eyes must be performed prior to any assessment requiring administration of eye drops to dilate the eyes, or any assessment requiring contact

Document: TDOC-0054099 **Version:** 2.0; Most-Recent; Effective; CURRENT

Status: Effective Page 45 of 71

with the eye. When assessing BCDVA, refractive correction is required. All visual acuity tests will be conducted in the photopic lighting conditions. Lighting measurement and manifest refraction details are provided in the MOP.

Visual acuity must be obtained by study personnel who have been successfully trained. For Preoperative Visit (Visit 0), data from the Investigator's previous routine cataract evaluation may be used, if the data 1) meet the requirements of this protocol and MOP, and 2) were collected less than 2 months before the ICF signed for the study.

10.2.10 Binocular Defocus Curve: Effectiveness Assessment

Defocus assessment requires the subject's best distance correction be varied from +2.00 D to -5.00 D in 0.50 D increments. The purpose of the defocus evaluation is to compare binocular clinical performance to the theoretical lens design. Defocus curve is commonly used clinical endpoints to evaluate the effectiveness of presbyopia correcting intraocular lenses, as well as with visual acuity.

10.2.12 Photopic Best Corrected Contrast Sensitivity: Effectiveness Assessment

Photopic best corrected contrast sensitivity with and without glare test will be conducted to assess the effect on visual quality of the trifocal IOL at distance.

10.2.13 Subjective symptoms: Effectiveness Assessment

Provide the subject the patient satisfaction questions prior to seeing a physician or any clinical exam. Assess the subjective visual status/satisfaction on daily activities.

10.2.14 Adverse Events including Secondary Surgical Interventions: Safety Assessment

Assess and record any adverse events that are observed or reported, including those associated with changes in concomitant medication dosing since the previous visit.

Document: TDOC-0054099 **Version:** 2.0; Most-Recent; Effective; CURRENT

Status: Effective Page 46 of 71

10.2.15 Device Deficiencies: Safety Assessment

Assess and record any device deficiencies that are reported or observed, including those associated with changes in concomitant medication dosing since the previous visit.

Requirements for reporting device deficiencies in the study can be found in Section 11.

Note: AEs and device deficiencies must be recorded for all enrolled subjects from the time of signature of informed consent, regardless of subject enrollment status (screen failure or included).

10.2.16 Slit-Lamp Examination: Safety Assessment

SLE of the cornea, iris/anterior chamber, and lens must be performed in both eyes before instillation of any diagnostic eye drops. For Preoperative Visit (Visit 0), data from the Investigator's previous routine cataract evaluation may be used, if the data 1) meet the requirements of this protocol and MOP, and 2) were collected less than 2 months before the ICF signed for the study.

Note: This exam must be completed by a medical doctor, or Ophthalmological technician.

10.2.17 Fundus examination and Fundus Visualization: Safety Assessment

For fundus examination, document the assessment of vitreous, retina, macula, choroid, optic nerve, and cup/disc ratio.

For fundus visualization, document whether the lens causes any difficulty in viewing and/or examining the retina or posterior segment, or affects the surgeon's ability to administer vitreal/retinal treatments, as compared to experience with monofocal IOLs. For Preoperative Visit (Visit 0), data from the Investigator's previous routine cataract evaluation may be used, if the data 1) meet the requirements of this protocol and MOP, and 2) were collected less than 2 months before the ICF signed for the study.

Note: This exam must be completed by a medical doctor, or Ophthalmological technician.

10.2.18 Subjective PCO including Posterior Capsulotomy: Safety Assessment

During the slit-lamp examination, assess the presence of PCO. For posterior capsulotomy assessment, indicate whether a posterior capsulotomy was performed since the last visit.

Document: TDOC-0054 099 **Version:** 2. o; Most-Recent; Effective; CURRENT

Status: Effective Page 47 of 71

10.2.19 IOL Position Change: Safety Assessment

After surgely, examine the IOL with the slit-lamp. Indicate whether the lens has changed position, tilted, or decentered since the last visit.

10.2.20 Other Surgical Procedures: Safety Assessment

During cataract surgely, document whether any additional procedures (eg, anterior vitrectomy, capsular tension ring) were performed. Evaluate whether the procedure meets the definition of an AE and repoltaccordingly.

10.2.21 Problems during Surgery: Safety Assessment

Document whether any problems arose during surgely. Examples of problems include anterior capsular tear, intraoperative loss of pupil dilation, bag-sulcus haptic placement. Evaluate whether the problem meets the definition of an AE and rep01t accordin gly.

10.2.22 Surgical Report: Safety Assessment

Implant the lens via clear cornea incision using the surgeon's standard operating procedures and in accordance with IOL directions for use. Keep an accurate and complete operative repolt in the source documentation.

10.2.23 Lens Information: Safety Assessment

Post lens implantation, retain the IOL adhesive label in the subject source.

10.2.24 Intraocular Pressure: Safety Assessment

Intraocular pressure must be measured in both eyes following Investigator's standard of care. Within a single subject utilize the same instmment type to measure IOP during each visit. Record the measurement in mmHg. For Preoperative Visit (Visit 0), data from the Investigator's previous routine cataract evaluation may be used, if the data 1) meet the requirements of this protocol and MOP, and 2) were collected less than 2 months before the ICF signed for the study.

10.3 Unscheduled Visits

If a subject visit occurs between any regularly scheduled visits, this visit must be documented as an Unscheduled Visit. During all unscheduled visits, the Investigator must conduct the following procedures:

• Record changes in medical condition or concomitant medication

Document: TDOC-0054 099 **Version:** 2. 0; Most-Recent; Effective; CURRENT

Status: Effective Page 48 of 71

- Collect Adverse Event inf01mation
- Record secondaly surgical interventions that have occurred since surgely, if applicable.
- Evaluate and record any device deficiencies.

The Investigator may perform additional procedures for proper diagnosis and treatment of the subject as below. The Investigator must document this info1mation in the subject's case hist01y source document s.

- Perform manifest refraction
- Perform slit-lamp examination including IOL obselvations (if any).
- Obse1ve any IOL position changes (ie, tilt and decentration) occurring since the previous visit. [Both Eyes, Bilateral]
- Assess subjective PCO, and record information for any PC that has occmTed since surgery, if applicable. [Both Eyes, Bilateral]
- Perform tonometry to measure IOP.

If during an Unscheduled Visit, the subject is discontinuing the IP or discontinuing from the study, the Investigator must conduct Exit procedures (refer to Visit 4A for the exit procedure) according to Table 3-1 Schedule of Study Procedures and Assessments and Section 10.4.3, as possible.

10.4 Directions Related to Secondary Surgical Intervention

This section is intended to provide guidance on the documentation and procedures related to SSis in this investigation. The investigator must consider subject complains and clinical outcome in his or her consideration of the need for a SSI, determine whether the cause of a needed SSI is due to optical properties of the IOL, and repoltfindings to the Sponsor with defined timelines in Section in the Section 11.3 Procedure for Recording and Rep01ting.

The main procedural steps in the decision process for SSis and notification to the Sponsor are detailed below:

- 1. The Investigator must detel mine whether an SSI is related to the optical properties of the IOL.
- 2. Any SSI (other than posterior capsulotomy laser treatment) perf01med for any reason should be recorded as a serious adverse event and reported to the Sponsor within 24 hours of its occmTence.

Document: TDOC-0054099 **Version:** 2.0; Most-Recent; Effective; CURRENT

Status: Effective Page 49 of 71

Note: If the SSI is a lens exchange or repositioning, the subsequent study post-operative visits should be based on the date of its surgery. Unscheduled Visit Case Report Forms (CRFs) should be used for other post-operative follow-up visits, where applicable. If the study lens is exchanged and replaced with a non-study lens, the subject will be required to complete all original subsequent study lens visit through Visit 4A (3 months).

Evaluation of Need for a Secondary Surgical Intervention:

The Need for consideration of an SSI includes one or more of the followings:

- 1. An Investigator assessment of subject's clinical outcome
- 2. A subject spontaneously complaining about visual symptoms to the investigational site personnel
- 3. Other reason(s) for an SSI, e.g. retained lens fragments

The Investigator should perform a thorough evaluation including diagnostic testing as needed and a subject interview to understand subject observations in detail to determine if an SSI is the appropriate treatment for the subject's undesired outcome (e.g., blurred vision, visual disturbances/distortions, or other reasons). Case management should be based on the Investigator's clinical assessment with consideration of the subject's postoperative UCDVA, BCDVA, IOL stability after implantation, and any subjective complaints. Careful consideration of the potential risks and benefits associated with the SSI for the subject is required, and these should be discussed with the subject prior to reposition or explant the IOL or otherwise surgically intervene.

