Safety: All adverse events (ocular and nonocular, serious and nonserious) including secondaly surgical interventions (SSis) related to the optical propeliies of the IOL for either eye. Device deficiencies Posterior capsule opacification Posterior capsulotomy IOL position change (tilt and decentration) Intraocular pressure Surgical problems Effectiveness: Assessment(s) All the effectiveness assessments will be conducted in photopic lighting conditions except the subjective symptoms assessment. Distance VA(4 m), Monocular (1st and/or 2nd eye) UCDVA Binocular UCDVA Binocular BCDVA Intelmediate VA (60 cm) Monocular (1st and/or 2nd eye) UCIVA Binocular UCIVA Near VA (40 cm) Monocular (1st and/or 2nd eye) UCNVA Binocular UCNVA Binoc ular defocus curve Best conected binocular contrast sensitivity with & without glare Subjective symptoms

Document: TDOC-0054 099 **Version:** 2. 0; Most-Recent; Effective; CURRENT

Status: Effective Page 15 of 71

~ THE COLLY C	1 age 13 01 71					
	Safety					
	Adverse DeviceEvents including Secondaly Surgical Interventions (SSis) related to the optical propeliies of the IOL					
	Device deficiencies					
	Fundus examination and fundus visualization					
	Intraocular pressure					
	Slit-lamp examination					
	IOL observations					
	Surgical problems					
	Subjective posterior capsule opacification					
	Posterior capsulotomy					
	Lens decentration and tilt					
Study Design	This is a prospective, single aim, unmasked, non-randomized, multi-					
	center study. Study subjects will be followed for 90-120 days.					
Subject	The study population consists of adult Korean males and females, at					
population	least 20 years of age or older at the time of screening, with no ocular					
	pathology that could confound study outcomes, who require cataract extraction in both eyes and desire an IOL that provides the potential					
	for near, intel mediate, and distance vision.					
Key inclusion	 Adults, at least 20 years of age or older at the time of screening, 					
criteria	of either gender in Korea, who require cataract extraction in both					
(See Section 8.1	eyes.					
for a complete list	Clear intraocular media other than cataract in both eyes.					
of inclusion	• Calculated lens power between+16.0 and +24.0 D.					
criteria)	Preoperative OR expected postoperative regular corneal					
	astigmatism of < 1.00 D.					
Voy oralisis						
Key exclusion criteria	Pregnancy or lactation					

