Rate of SSIs related to the optical properties of the IOL for either eye during the study will be summarized by eye. All AEs will be coded using the Medical Dictionary for Regulatory Activities (MedDRA) and will be presented by severity (mild, moderate, or severe) and relationship to the test product. Device deficiencies, posterior capsule opacification, posterior capsulotomy, surgical problems, and IOL position change (tilt and decentration) will be summarized descriptively. Intraocular pressure at each visit and change from baseline will be summarized accordingly,

Assuming a standard deviation of 0.17 logMAR with defocus visual outcomes, 40 subjects will have more than 99% probability to observe the half width of 90% two-sided confidence interval will be no more than 0.06 logMAR at each defocus. The precision of estimates are within ± 3 letters with visual outcomes.

Assuming a dropout rate of 10% at Month 3, approximately 44 subjects will be bilaterally implanted to ensure that data for at least 40 subjects is available at Month 3.

Clinical trial duration

- a. Total expected duration of the clinical investigation: approximately 12 months
- b. Expected duration of each subjects' participation : approximately between 3 ~7 months

Alcon - Business Use Only Protocol - Clinical Effective Document: TDOC-0054099 Version: 2.0; Most-Recent; Effective; CURRENT Effective Date: 13-Dec-2017

Page 19 of 71 Status: Effective

	 c. Planned follow-up duration: about 3 – 4 months post 2nd eye implantation d. Enrollment period: approximately 5 months (The recruit period can be extended if 44 bilaterally implanted subjects cannot achieve 40 evaluable due to unilateral implantation or exclusion after screening visit.).
Key words	Prospective, Single Arm, Unmasked, Non-Randomized, Multi-Center Study, Cataract, Bilateral implantation, The ACRYSOF IQ PanOptix Presbyopia Correcting IOL, Model TFNT00, Trifocal, Korea
Associated materials	Biohazard labeled bag

.:; € □

a t, et

Inclusion/Exclusion

Administer Treatment(s) 0_hthalmic Assessments Distance VA at 4 m х9 х6 х6 Monocular Unconected xio Bino cular Uncon e cte d X Monocular Best X Conected Binocular Best X X X Conected Intermediate VA at 60 cm

Χ

Χ

Χ

Table 3-1	Schedule of Study Procedures and Assessments
	1 Operative Eye

		10	perative	Eye	2n _O	perati ve	Eye	Both	Eyes	

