- 2. Visit 00A (2nd eye surgery) must occur after a minimum of 2 calendar days and a maximum of 30 calendar days after Visit 00.
- 3. If necessary, Visit 4A may be completed over 2 days within a two-week period. Both days must fall within the specified visit window.

4. In women of child-bearing potential only.

- Data is reported in EDC at the surgical visit, but may be collected at a previous visit.
- Testing is conducted monocular bilaterally.
- Only measure in case considered necessary per the investigator's medical opinion.
- Collected from time of consent onward.
- 9. 1st operative eye.
- 10. 2nd operative eye.

Document: TDOC-0054099
Status: Effective

Version: 2.0; Most-Recent; Effective; CURRENT

Document: TDOC-0054099 **Version:** 2.0; Most-Recent; Effective; CURRENT

Status: Effective Page 24 of 71

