7 INVESTIGATIONAL PLAN

7.1 Study Design

This is a prospective, single-arm, unmasked, non-randomized, multi-center study of the ACRYSOF IQ PanOptix Presbyopia Correcting IOL, Model TFNT00.

Both eyes of a subject must require cataract surgery to qualify for enrollment into this study.

The first operative eye is defined as the eye with the worse BCDVA at screening visit. If BCDVA is the same in both eyes, identify the right eye (OD) as the first operative eye. The second eye implant can occur according to each participating site's standard visit schedule; however, it must occur within 30 days of the first eye implant.

A total of 9 scheduled visits are planned (some scheduled visits may be conducted on the same day due to the visit window) and subject participation is expected to last 3-7 months. The visits include a Screening visit (Visit 0), 2 Operative Visits (Visit 00 and Visit 00A), and 6 postoperative visits at the following intervals: Day 1-2 (Visit 1/1A), Day 7-15 (Visit2/2A), Day 30-60 (Visit 3A), and Day 90-120 (Visit 4A) (See Figure 7-1 Study Design). Primary endpoint data will be collected at the Month 3 visit / Visit 4A (90-120 day post 2nd eye implantation).

[figure not shown]
Note: Visit 4A may be completed over 2 days within a 2-week period. Both days must fall within the specified visit window.

The schedule of visits is shown below:

Document: TDOC-0054099 Version: 2.0; Most-Recent; Effective; CURRENT

Status: Effective Page 33 of 71

Figure 7-1 Study Design

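### Does dating visits from a lens exchange or repositioning leave the primary Visit 4A without a usable date?

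*Protocol*

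**What the plan says.** The note in Protocol 10.4 has three parts.

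- The rule: "If the SSI is a lens exchange or repositioning, the subsequent study post-operative visits should be based on the date of its surgery".
- Other follow-up visits after the operation go on the forms for unscheduled visits, where applicable.
- A separate provision for a study lens that is "exchanged and replaced with a non-study lens, the subject will be required to complete all original subsequent study lens visit through Visit 4A".

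The general schedule has a fixed anchor. Protocol 7.1 states: "Primary endpoint data will be collected at the Month 3 visit / Visit 4A (90-120 day post 2nd eye implantation". Table 3-1 and SAP Table 2 both head the Visit 4A column as 90-120 days after Visit 00A, the second-eye surgery. Note 3 to Table 3-1 lets Visit 4A be split over two days, with the condition "Both days must fall within the specified visit window".

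The stated durations are:

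- Protocol 7.1: "subject participation is expected to last 3-7 months".
- Protocol Summary: "Study subjects will be followed for 90-120 days", "Total expected duration of the clinical investigation: approximately 12 months" and "Enrollment period: approximately 5 months". The summary also allows recruitment to be extended.

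For the analysis, SAP 4.3.1 summarises the defocus curve at the visit it names Month 3 (Visit 4A). SAP 2.1 defines the full analysis set by successful bilateral implantation only. Protocol 12.1 leaves final evaluability to the Deviations and Evaluability Plan (DEP).

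**The concern.** A site following 10.4 would schedule the last visit from the date of the second operation. A site following 7.1 and Table 3-1 would schedule it from second-eye surgery. Neither the schedules nor the SAP refers to 10.4, and 10.4 does not refer to the Visit 4A window.

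Visit 4A carries the primary endpoint and is the last scheduled visit in the by-visit safety tables. A visit that is on time under one passage could be out of window under the other, and might be logged as a deviation when evaluability is settled. The dates also capture different stages of recovery. After an operation on day 60, the fixed window measures vision 30-60 days after that operation. The re-based window measures it 90-120 days after the operation, which is 150-180 days after Visit 00A. The stated participation and study durations, moreover, add up only on the fixed schedule.

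**Working it through.** **1. The plan's durations.** Inputs from the notes to Table 3-1: at most 60 days from Visit 0 to Visit 00, 2 to 30 days from Visit 00 to Visit 00A, and 90-120 days from Visit 00A to Visit 4A.

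- Minimum: 0 + 2 + 90 = 92 days, about 3 months.
- Maximum: 60 + 30 + 120 = 210 days, which is 7.0 months of 30 days (6.9 at 30.44 days per month).
- Study length: 5 months of enrollment + 7 = 12 months.

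Both stated durations are reproduced on the fixed schedule.

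**2. Overlap of the two windows.** Let s be the day of the operation after Visit 00A. The documents give no timing, so s is a free assumption. The re-based window is s+90 to s+120. It shares max(0, 31 − s) days with 90-120.

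| s | Re-based window (days after 00A) | Shared days | Maximum participation, 210 + s |
|---|---|---|---|
| 10 | 100-130 | 21 | 220 days |
| 30 | 120-150 | 1 | 240 days (7.9 months) |
| 31 | 121-151 | 0 | 241 days (7.9 months) |
| 60 | 150-180 | 0 | 270 days (8.9 months) |
| 119 | 209-239 | 0 | 329 days (10.8 months) |

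The last row applies because Visit 4A may be as late as day 120, so an operation on days 90-119 can still precede it. Study length in that extreme is 5 + 10.8 = 15.8 months. This needs a late operation in a last-enrolled subject who uses every window in full.

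**3. Which record is analysed.** Put together, the passages give an answer:

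- 10.4 says the remaining study visits are still made, dated from the operation. They therefore keep their names, and other visits go on unscheduled forms.
- SAP 4.3.1 takes the record by its name, Visit 4A.
- SAP 2.1 has no visit-window condition. Protocol 12.2 adds only that bilateral defocus measurements exist.

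A subject followed under 10.4 thus yields one record called Visit 4A, and it enters the primary summary unless the DEP says otherwise.

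**4. Size.** The half-width is t(0.95, n−1) × 0.17 / √n, with the SD of 0.17 logMAR from the sample size section.

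- n = 40: 1.6849 × 0.17 / 6.3246 = 0.0453
- n = 39: 1.6860 × 0.17 / 6.2450 = 0.0459

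The plan claims more than 99% probability of a half-width of at most 0.06. That probability is 0.9975 at n = 40, 0.9958 at n = 39 and 0.9931 at n = 38. It falls below 99% only at n = 37 (0.9890), so the claim survives the loss of two records.

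If the record is kept, suppose the two dates differ by 0.2-0.4 logMAR in one of 40 subjects (an assumption; the documents give no figure). The mean moves by 0.2/40 to 0.4/40 = 0.005-0.010 logMAR. At the plan's 0.06 = 3 letters, or 0.02 per letter, that is 0.25-0.5 letter.

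**The case for a change.** The strongest case for a change concerns data collection. The unscheduled-visit procedures in Protocol 10.3 do not list the defocus curve, and SAP Table 2 shows it only at Visits 3A and 4A. If a site treats a late visit as unscheduled, the primary measurement may not be taken. Reading 10.4 as an exception is also an inference, because no passage says so. The last part of its note keeps the original visits for exchange to a non-study lens, while its first sentence covers every exchange.

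Part of this stands. For repositioning, and for exchange to another study lens, from day 31 onward no day satisfies both passages as literally written, and no cross-reference settles it.

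The rest is weaker. A site applying 10.4 would perform a study visit, with its scheduled tests, not an unscheduled one. Note 3 confines a two-day visit to its window and does not say which anchor applies after a second operation. SAP 1.1.1 counts from bilateral implantation without naming the second eye. The durations are worded as approximate or expected, and recruitment may be extended, so an exceptional subject does not breach them.

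**Conclusion.** No change to the plan follows. The passages differ and do not refer to each other, but a specific rule for an unusual event beside a general schedule is a gap that analysts fill sensibly. The visit is made, it keeps its name, and the SAP selects by that name. Writing a cross-reference or adding dates to a listing would be tidy. It would not alter a result: the study is descriptive, with no hypothesis or success criterion, and losing one record costs 0.0006 logMAR of half-width (0.0459 − 0.0453). Individual effectiveness listings (SAP 4.3) and a listing of secondary interventions by subject, visit and eye (SAP 5.3.2) are already planned, so any affected subject can be identified.

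This rests on few subjects being affected, since no rate is given, and on the DEP not contradicting the reading above. The DEP and the manual of procedures were not available, part of the SAP is hidden, and the SAP cites protocol Version 1.0 whereas Version 2.0 was reviewed. No view is taken on which date is right.
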